5.1.2.9 Management of Increases in QT Interval

Study drug should be discontinued in patients who develop any of the following, unless there is a clear alternative cause for the changes:

- Sustained (at least two ECG measurements >30 minutes apart) QTcF that is >500 ms and >60 ms longer than the baseline value
- Sustained absolute QTcF that is >515 ms
- An episode of torsades de pointes or a new ECG finding of clinical concern

Of note, if there is a new intraventricular conduction block, the increase in QRS complex duration should be subtracted from the QTcF change, because this represents an increase in QTcF unrelated to alterations in repolarization. Also of note, it is not uncommon to record arrhythmias such as non-sustained ventricular tachycardia, supraventricular tachycardia, pauses, or atrial fibrillation in healthy volunteers receiving placebo during periods of extended ECG monitoring. Therefore, it is critical that expert cardiology advice be sought to confirm any ECG changes and to ascertain the likelihood of a drug-induced arrhythmia versus the background occurrence of this arrhythmia. In such a situation, saving all available ECG data is highly suggested.

Management of patients with sustained QTcF prolongation should include close monitoring, with ECGs repeated at least hourly until two successive ECGs show resolution of the findings, correction of any electrolyte abnormalities, and possible discontinuation of other concomitant medications that are known to prolong the QT interval. Consultation with a cardiologist or electrophysiologist is recommended, to help in the management of such patients. The Medical Monitor should be notified as soon as possible.

In rare circumstances, it may be acceptable to resume study drug, at a lower dose, provided that any ECG abnormalities have resolved and the patient is appropriately monitored. Clinical judgment should be applied.

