4.5.13 Electrocardiograms

ECG recordings will be obtained at specified timepoints, as outlined in the schedule of activities (see [REDACTED]). ECGs acquired on different days should be as closely time-matched as feasible. Single ECG recordings may be additionally obtained at unscheduled timepoints as indicated.

Lead placement should be as consistent as possible. ECG recordings must be performed after the patient has been resting for at least 10 minutes. All ECGs are to be obtained prior to other procedures scheduled at that same time (e.g., vital sign measurements, blood draws) and should be obtained around the same time after any meal, preferably after a minimum of 3 hours. Circumstances that may induce changes in heart rate, should be avoided during the pre-ECG resting period and during ECG recording.

For safety monitoring purposes, the investigator must review, sign, and date all ECG tracings. Paper copies of ECG tracings will be kept as part of the patient's permanent study file at the site. The following should be recorded in the appropriate eCRF: heart rate, RR interval, QRS interval, PR duration, uncorrected QT interval, and QTcF based on the machine readings of the individual ECG tracings. Any morphologic waveform changes or other ECG abnormalities must be documented on the eCRF. If considered appropriate by the Sponsor, ECGs may be analyzed retrospectively at a central laboratory.

If at a particular post-dose timepoint the mean QTcF is >500 ms and/or 60 ms longer than the baseline value, another ECG must be recorded, ideally within the next 5 minutes, and ECG monitoring should continue until QTcF has stabilized on two successive ECGs. The Medical Monitor should be notified. Standard-of-care treatment may be instituted per the discretion of the investigator. If a PK sample is not scheduled for that timepoint, an unscheduled PK sample should be obtained. A decision on study drug discontinuation should be made, as described in Section [4.6.1](#). The investigator

should also evaluate the patient for potential concurrent risk factors (e.g., electrolyte abnormalities, co-medications known to prolong the QT interval, severe bradycardia).

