4.6 TREATMENT, PATIENT, STUDY, AND SITE DISCONTINUATION

4.6.1 Study Treatment Discontinuation

Patients must permanently discontinue study treatment if they experience any of the following:

- Any medical condition that the investigator or Sponsor determines may jeopardize the patient's safety if he or she continues to receive study treatment
- Investigator or Sponsor determination that treatment discontinuation is in the best interest of the patient
- Pregnancy
- Any adverse event CTCAE Grade 4 or higher, regardless of attribution to study drug
- Positively detected suicidal ideation type 4 or 5 or suicidal behavior
- 24-hour urinary cortisol $>1.5 \times$ ULN and $>2 \times$ baseline, if confirmed on follow up visit within 2 weeks.
- If any signs or symptoms of hyper- or hypothyroidism that accompany changes in thyroid function tests (TSH or free T4) that are confirmed by repeat testing.
- Abnormal IGF-1 that is confirmed by repeat testing.
- Nontraumatic bone fracture

The primary reason for study treatment discontinuation should be documented on the appropriate eCRF. Patients who discontinue study treatment prematurely will not be replaced. Patients who discontinue treatment prior to study treatment completion will participate in the end-of-treatment visit at the time of early discontinuation and will enter a follow-up period for a total of 6 weeks.

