5.1.2 Management of Patients Who Experience Adverse Events

5.1.2.1 Dose Modifications

In the fixed dose arms, there will be no dose modifications (dose reductions) for BFKB8488A or placebo in this study due to adverse events in individual patients. [REDACTED]

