5.2.3 Adverse Events of Special Interest (Immediately Reportable to the Sponsor)

Adverse events of special interest are required to be reported by the investigator to the Sponsor immediately (i.e., no more than 24 hours after learning of the event; see Section 5.4.2 for reporting instructions). Adverse events of special interest for this study are as follows:

- Marked hypertension as defined by a systolic blood pressure ≥ 180 mm of Hg that is at least 20 mm higher than the baseline measurement.
- Weight loss greater than 10% of baseline (Day 1) body weight within a 12-week period at any point in the study
- Glucose measurements, serum or home glucometer readings, ≤ 54 mg/dL
- Symptomatic hypoglycemia causing altered mental status, seizures, or requiring IV dextrose for treatment
- Increases in QT interval, unless there is a clear alternative cause for the changes
 - Sustained (at least 2 ECG measurements > 30 minutes apart) QTcF that is > 500 ms and/or > 60 ms longer than the baseline value
 - Sustained absolute QTcF that is > 515 ms

An episode of torsades de pointes or a new ECG finding of clinical concern
- Cases of potential drug-induced liver injury that include an elevated ALT or AST in combination with either an elevated bilirubin or clinical jaundice, as defined by Hy's Law (see Section 5.3.5.7)
- Suspected transmission of an infectious agent by the study drug, as defined below

Any organism, virus, or infectious particle (e.g., prion protein transmitting transmissible spongiform encephalopathy), pathogenic or non-pathogenic, is

considered an infectious agent. A transmission of an infectious agent may be suspected from clinical symptoms or laboratory findings that indicate an infection in a patient exposed to a medicinal product. This term applies only when a contamination of the study drug is suspected.

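### The ECG section sends QTc stopping decisions to a list with no QTc criterion, and lower-dose resumption after a QTc event conflicts with the no-reduction rule in the fixed dose arms

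*Combined protocol and SAP*

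**What the plan says.** **Trigger and pointer.** Protocol Section 4.5.13 sets the condition for a further ECG: "If at a particular post-dose timepoint the mean QTcF is >500 ms and/or 60 ms longer than the baseline value". It then continues: "A decision on study drug discontinuation should be made, as described in Section" 4.6.1. Section 5.1.2.3 also points to Section 4.6.1, describing it as the detailed list of events that require stopping.

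**The list pointed to.** Section 4.6.1 opens: "Patients must permanently discontinue study treatment if they experience any of the following". Nine bullets follow. Two rest on investigator or sponsor judgement about safety or the patient's interest. The others are pregnancy, any adverse event of Grade 4 or higher, suicidality, urinary cortisol, thyroid changes with symptoms, IGF-1 and non-traumatic fracture.

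**The QTc criteria.** Section 5.1.2.9 says study drug should be stopped, unless another cause is clear, for any of three findings. The first is "Sustained (at least two ECG measurements >30 minutes apart) QTcF that is >500 ms and >60 ms longer than the baseline value". The second sets a limit that does not depend on baseline: "Sustained absolute QTcF that is >515 ms". The third is torsades or a new ECG finding of concern. The section closes by saying that, in rare cases and once ECG abnormalities have resolved, "it may be acceptable to resume study drug, at a lower dose".

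**The dosing rule.** Section 5.1.2.1 states, for the fixed dose arms, that "there will be no dose modifications (dose reductions) for BFKB8488A or placebo in this study due to adverse events in individual patients". The text after that sentence is blacked out.

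**The concern.** A site facing an abnormal QTcF needs to know whether to stop, whether stopping is permanent, and at what dose treatment may resume. The sections give different answers depending on where the site starts reading.

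A site that follows Section 4.5.13 arrives at a list of permanent discontinuations with no QTc threshold. A site that reads Section 5.1.2.9 finds numeric thresholds, an exception for alternative causes and a route back to treatment. The difference also affects follow-up. Under Section 4.6.1 the patient has the end-of-treatment visit early and enters the 6-week follow-up; under Section 5.1.2.9 the patient may return to dosing.

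For a fixed-dose patient who does return, Section 5.1.2.9 contemplates a lower dose and Section 5.1.2.1 excludes it. The fixed dose arms exist to compare 50, 75 and 100 mg with placebo. Section 6 groups the efficacy population by randomized assignment, so a patient resumed at a lower dose would still count under the assigned one.

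**Working it through.** There is no planned figure to reproduce. The check compares the texts and then tests the QTcF thresholds for logical conflict.

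**1. Does the pointer lead to the criteria?**

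| Feature | Section 4.6.1 (where 4.5.13 points) | Section 5.1.2.9 |
|---|---|---|
| QTcF threshold | none | two numeric criteria |
| Torsades or ECG finding | not named | named |
| Force | must, permanent | should |
| Alternative-cause exception | none | yes |
| Resumption | excluded by the word permanent | possible in rare cases |

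Other stopping rules in Section 5.1.2 are repeated in Section 4.6.1: non-traumatic fracture (5.1.2.5), cortisol, IGF-1 and thyroid (5.1.2.7), and suicidality (5.1.2.8). The QTc rule is not. So the pointer fails, and the two sections differ on permanence.

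**2. Can the two dosing sentences both hold?** Section 5.1.2.1 covers the fixed dose arms: 20 + 60 + 60 + 40 = 180 planned patients (Section 6.1). Section 5.1.2.9 names no arm, so it includes those patients. A QTc event is an adverse event in an individual patient. For the fixed dose arms, one sentence permits what the other excludes. The rule for the other cohort is redacted, so nothing can be said about it.

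**3. Do the QTcF thresholds conflict?** Section 5.2.3 makes reportable a sustained "QTcF that is > 500 ms and/or > 60 ms longer than the baseline value". Let A be QTcF above 500 ms, B a rise above 60 ms, and C QTcF above 515 ms.

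- Stop (5.1.2.9): (A and B) or C.
- Report as an adverse event of special interest (5.2.3): (A or B) or C.
- Repeat ECG (4.5.13): A, or a rise of 60 ms (taken as 60 ms or more).

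(A and B) implies (A or B), and C implies A. Every stopping value is therefore also a reporting value and a repeat-ECG value. Checking every whole-millisecond QTcF up to 600 ms, for nine baselines from 380 to 470 ms, found no exception. The values that are reportable but meet neither numeric stopping criterion are:

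| Baseline (ms) | Reportable, not a numeric stop (ms) |
|---|---|
| 400 | 461–500 |
| 420 | 481–500 |
| 440 | none |
| 450 | 501–510 |
| 460 or 470 | 501–515 |

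For example, from a baseline of 400 ms a sustained 465 ms is a rise of 465 − 400 = 65 ms: reported, but not stopped on this criterion. The rules are nested and no ECG receives opposite instructions.

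**The case against.** **The pointer.** The best defence is that no rule is missing. Section 4.5.13 asks for a decision, and Section 4.6.1 has judgement-based bullets and a Grade 4 bullet under which a QTc event could fall. Section 4.3.2 separately sends sites to Section 5.1.2 for interruption and discontinuation guidance, where the QTc criteria have their own heading. Because they allow resumption, leaving them off a permanent list may be deliberate; the liver-enzyme rules in Table 1, which allow interruption, are not on it either. This is fair: it makes the first conflict a misdirected reference rather than an absent rule. It does not remove the conflict, because Section 4.5.13 names Section 4.6.1 for this very decision and Section 5.1.2.3 presents that list as the detailed one.

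**The dose.** The lower-dose sentence may have been written for the variable-dose arm mentioned in Sections 3.3.3 and 6.4.1. That is possible, but the sentence does not say so. The defence does limit the point to the fixed dose arms. The analysis effect is also small: resumption is described as rare, and grouping by assignment is the stated efficacy rule. Safety and PK analyses group by treatment received (Sections 6.5 and 6.6), although the protocol does not say where a patient who received two doses would fall.

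**A stronger reading.** A reader might infer that *and* in the stopping rule contradicts *and/or* in the repeat-ECG and reporting rules. It does not: the three rules govern different actions and are nested. Sections 5.1.2.9 and 5.2.3 are otherwise nearly the same text, so it is reasonable to ask whether the difference is intended, but no more than that.

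A reader might also note that from a baseline of 455 ms a rise above 60 ms exceeds 455 + 60 = 515 ms, so the first stopping criterion then adds nothing to the second. Given the entry limits in Section 4.1.2 (450 ms for men, 470 ms for women), this concerns only women with a baseline of 455–470 ms. It shows redundancy within a list of alternatives, not a conflict, and the third criterion and the judgement bullets in Section 4.6.1 still apply.

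**Conclusion.** Two conflicts hold on the visible text. Section 4.5.13 sends the QTc stopping decision to a permanent-discontinuation list without QTc criteria, while the criteria in Section 5.1.2.9 carry an exception and possible resumption. For the fixed dose arms, the lower-dose sentence in Section 5.1.2.9 is incompatible with Section 5.1.2.1.

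The size is modest in statistical terms and cannot be put as a number of patients, since the documents give no expected frequency of QTc events. The dosing conflict applies in principle to the whole fixed dose cohort of 180. Its practical weight is that a safety instruction must be usable when an abnormal ECG appears, so it should be corrected.

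The conclusion assumes that the redacted text after the fixed-dose sentence in Section 5.1.2.1 does not make an exception for those arms; that sentence itself is complete. It does not extend to the other cohort, and it makes no judgement on any threshold, dose or stopping rule.

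**What to change.** - Reconcile Sections 4.5.13, 4.6.1 and 5.1.2.3 with Section 5.1.2.9, so that the reference in the ECG section leads to the QTc criteria and the text is consistent on whether stopping for QTc is permanent or can be followed by resumption.
- Reconcile the lower-dose sentence in Section 5.1.2.9 with Section 5.1.2.1 for the fixed dose arms. If lower-dose resumption remains possible there, the data analysis plan should say how those patients are presented.
- Have the sponsor confirm that the difference in connective between Section 5.1.2.9 and Sections 4.5.13 and 5.2.3 is intended.

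The clinical team decides which rule applies in each case. The cost is wording and cross-reference changes in an amendment; sample size and the planned comparisons do not change.

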5.2 SAFETY PARAMETERS AND DEFINITIONS

Safety assessments will consist of monitoring and recording adverse events, including serious adverse events and adverse events of special interest, performing protocol-specified safety laboratory assessments, measuring protocol-specified vital

signs, and conducting other protocol-specified tests that are deemed critical to the safety evaluation of the study.

Certain types of events require immediate reporting to the Sponsor, as outlined in Section [5.4](#).

5.2.1 Adverse Events

According to the ICH guideline for Good Clinical Practice, an adverse event is any untoward medical occurrence in a clinical investigation subject administered a pharmaceutical product, regardless of causal attribution. An adverse event can therefore be any of the following:

- Any unfavorable and unintended sign (including an abnormal laboratory finding), symptom, or disease temporally associated with the use of a medicinal product, whether or not considered related to the medicinal product
- Any new disease or exacerbation of an existing disease (a worsening in the character, frequency, or severity of a known condition) (see Section [5.3.5.9](#) and [5.3.5.10](#) for more information)
- Recurrence of an intermittent medical condition (e.g., headache) not present at baseline
- Any deterioration in a laboratory value or other clinical test (e.g., ECG, X-ray) that is associated with symptoms or leads to a change in study treatment or concomitant treatment or discontinuation from study drug
- Adverse events that are related to a protocol-mandated intervention, including those that occur prior to assignment of study treatment (e.g., screening invasive procedures such as biopsies)

5.2.2 Serious Adverse Events (Immediately Reportable to the Sponsor)

A serious adverse event is any adverse event that meets any of the following criteria:

- Is fatal (i.e., the adverse event actually causes or leads to death)
- Is life threatening (i.e., the adverse event, in the view of the investigator, places the patient at immediate risk of death)

This does not include any adverse event that, had it occurred in a more severe form or was allowed to continue, might have caused death.

- Requires or prolongs inpatient hospitalization (see Section [5.3.5.11](#))
- Results in persistent or significant disability/incapacity (i.e., the adverse event results in substantial disruption of the patient's ability to conduct normal life functions)
- Is a congenital anomaly/birth defect in a neonate/infant born to a mother exposed to study drug

- Is a significant medical event in the investigator's judgment (e.g., may jeopardize the patient or may require medical/surgical intervention to prevent one of the outcomes listed above)

The terms "severe" and "serious" are not synonymous. Severity refers to the intensity of an adverse event (e.g., rated as mild, moderate, or severe, or according to National Cancer Institute Common Terminology Criteria for Adverse Events [NCI CTCAE]; see Section 5.3.3); the event itself may be of relatively minor medical significance (such as severe headache without any further findings).

Severity and seriousness need to be independently assessed for each adverse event recorded on the eCRF.

Serious adverse events are required to be reported by the investigator to the Sponsor immediately (i.e., no more than 24 hours after learning of the event; see Section 5.4.2 for reporting instructions).

5.2.3 Adverse Events of Special Interest (Immediately Reportable to the Sponsor)

Adverse events of special interest are required to be reported by the investigator to the Sponsor immediately (i.e., no more than 24 hours after learning of the event; see Section 5.4.2 for reporting instructions). Adverse events of special interest for this study are as follows:

- Marked hypertension as defined by a systolic blood pressure ≥ 180 mm of Hg that is at least 20 mm higher than the baseline measurement.
- Weight loss greater than 10% of baseline (Day 1) body weight within a 12-week period at any point in the study
- Glucose measurements, serum or home glucometer readings, ≤ 54 mg/dL
- Symptomatic hypoglycemia causing altered mental status, seizures, or requiring IV dextrose for treatment
- Increases in QT interval, unless there is a clear alternative cause for the changes
 - Sustained (at least 2 ECG measurements > 30 minutes apart) QTcF that is > 500 ms and/or > 60 ms longer than the baseline value
 - Sustained absolute QTcF that is > 515 ms

An episode of torsades de pointes or a new ECG finding of clinical concern
- Cases of potential drug-induced liver injury that include an elevated ALT or AST in combination with either an elevated bilirubin or clinical jaundice, as defined by Hy's Law (see Section 5.3.5.7)
- Suspected transmission of an infectious agent by the study drug, as defined below

Any organism, virus, or infectious particle (e.g., prion protein transmitting transmissible spongiform encephalopathy), pathogenic or non-pathogenic, is

considered an infectious agent. A transmission of an infectious agent may be suspected from clinical symptoms or laboratory findings that indicate an infection in a patient exposed to a medicinal product. This term applies only when a contamination of the study drug is suspected.

5.3 METHODS AND TIMING FOR CAPTURING AND ASSESSING SAFETY PARAMETERS

The investigator is responsible for ensuring that all adverse events (see Section 5.2.1 for definition) are recorded on the Adverse Event eCRF and reported to the Sponsor in accordance with instructions provided in this section and in Sections 5.4 – 5.6.

For each adverse event recorded on the Adverse Event eCRF, the investigator will make an assessment of seriousness (see Section 5.2.2 for seriousness criteria), severity (see Section 5.3.3), and causality (see Section 5.3.4).

5.3.1 Adverse Event Reporting Period

Investigators will seek information on adverse events at each patient contact. All adverse events, whether reported by the patient or noted by study personnel, will be recorded in the patient's medical record and on the Adverse Event eCRF.

After informed consent has been obtained but prior to initiation of study drug, only serious adverse events caused by a protocol-mandated intervention (e.g., invasive procedures such as biopsies, discontinuation of medications) should be reported (see Section 5.4.2 for instructions for reporting serious adverse events).

After initiation of study drug, all adverse events will be reported until 42 days after the final dose of study drug.

Instructions for reporting adverse events that occur after the adverse event reporting period are provided in Section 5.6.

5.3.2 Eliciting Adverse Event Information

A consistent methodology of non-directive questioning should be adopted for eliciting adverse event information at all patient evaluation timepoints. Examples of non-directive questions include the following:

"How have you felt since your last clinic visit?"

"Have you had any new or changed health problems since you were last here?"

